This is a pilot study that aims to compare treatment for obesity in adolescents delivered via a group telehealth model with treatment provided via our traditional in-clinic Empower weight management program, in order to assess feasibility, cost-effectiveness, and efficacy of group telehealth. We will assess efficacy by measuring: (1) Changes in BMI, blood pressure, and relevant laboratory values (2) Quality of life scores (3) Self-efficacy scores (4) Patient satisfaction. Subject recruitment and study design: Patients that have been referred to Empower and the KidsNFitness program will be eligible, as well as CHLA patients seen in a multitude of environments, including outpatient clinics, the Emergency Department, the inpatient setting seen by Physical Therapy, Occupational Therapy, and Clinical Nutrition. In order to be recruited to the intervention group, participants must be between 14 and 18 years of age; informed consent will be obtained. After obtaining their consent, intervention group participants will be assigned to the intervention telehealth group (final total n=32). We plan to run two consecutive 6-month cohorts. Each cohort will consist of two telehealth groups of 6-8 participants each (total 12-16). We plan to over-enroll each group to account for expected attrition; we will enroll a minimum of 6 and maximum of 8 participants in each of the two telehealth groups, for a total of approximately 30 participants (final total n=32) between the two 6-month cohorts. Parents will be contacted on a weekly basis to update them about their child's session attendance, the general content of the sessions, and to remind them to prompt their child to log on to their twice monthly telehealth sessions. We will ask for their preferred mode of contact (text message, email, and/or phone) and use all preferred methods to contact them. Intervention group subjects will be enrolled into a group telehealth program, in which twice monthly sessions will be held using a HIPAA compliant web-based platform, for 6 months.

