The intervention group will be asked to come in for in-person research visits at 0, 3 and 6 months for collection of weight, blood pressure, and other anthropometric measures; they will be asked to complete baseline, 3 month, and 6 month questionnaires regarding quality of life, self-efficacy, diet, and physical activity habits; an additional survey regarding satisfaction with treatment will be administered at end of the 6 month study period, and repeat bloodwork will be obtained at that time.

For the control group, we will use retrospective data for all eligible patients from our Empower clinic whose first clinic visit was between January 2015 and June 30, 2019. The end point for data collection will be no later than December 31, 2019. Those who are matched to the intervention group for age, gender, and severity of obesity; we will request a waiver of consent for this group.

Statistics and data analysis plans: The target recruitment of approximately 206 subjects (30 intervention and 176 control) was arrived at based on practicality and feasibility for a pilot study, and modified per recommendations of our current biostatistician, based on the limited data available upon chart review for many of the clinic control subjects. For evaluation of changes in the continuous outcomes, BMI, blood pressure, and hemoglobin A1C, triglyceride level, and ALT, assessed at baseline and immediately following the end of the 6 month intervention, we

will utilize regression analyses, which will allow us to compare the magnitude of change between the telehealth intervention and the comparison group, taking into account both change from baseline to follow-up time points as well as relevant baseline covariates. For these analyses covariates will be participants' age, gender, and presence of existing medical conditions (e.g. diabetes; rheumatologic conditions) that could affect weight loss.

Background

Prior Literature

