All study staff are HIPAA and CITI certified and will be trained in the use of the web-based platform. Additionally, all clinical staff conducting telehealth sessions will be oriented to the semi-structured curriculum, and the study coordinator who will also be conducting the intersession coaching will be trained and mentored by a CHLA researcher who has recently conducted a similar study utilizing a cell-phone based app and brief coaching for treatment of adolescents with obesity.

Subject Selection and Withdrawal

Inclusion Criteria

Prospective Group:

Youth age 14-18 who meet criteria for or are currently enrolled in the Empower weight management clinic will be included. These criteria include body mass index (kg/m2) that is either greater than the 99th percentile, or greater than the 95th percentile accompanied by an obesity-related comorbid condition such as hyperlipidemia, pre-diabetes or diabetes, non-alcoholic fatty liver disease (NAFLD), obstructive sleep apnea, or polycystic ovarian syndrome.

Youth will need to speak English but those whose parents' primary language is Spanish will be included.

Retrospective Control Group:

All eligible youth from our EMPOWER clinic patients whose first clinic visit occurred between January 2015 and June 30, 2019, and were 14-18 years old, were included in our control group.

Exclusion Criteria

Prospective Group: (1) significant intellectual or neurodevelopmental disability, ie previous diagnosis of autism spectrum disorder or developmental delay (2) non-English speaking; (3) age < 14 years and > 18 years (4) weight greater than 255 kg.

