(3) Parents will be contacted on a weekly basis to update them about their child's session attendance, the general content of the sessions, and to remind them to prompt their child to log on to their twice monthly telehealth sessions. We will ask for their preferred mode of contact (text message, email, and/or phone) and use all preferred methods to contact them.

- 4) All Telehealth sessions will be recorded. The recordings may include audio and video (only if the participants have their camera turned on during the session), and video of the research staff running the session. Participants will be reminded verbally before every session that they will be recorded.
 - Data collected on Experimental procedures for the telehealth group include:
 - 1. Data collection from Empower referral packets and/or the electronic medical record regarding their weight/body mass index (BMI), blood pressure, medications, and lab results, onto the CRFs. Date of study visit, and current zip code will be included, as well as preferred contact method for coaching (ie text, mobile phone, or electronic mail). If contact info itself (ie the actual mobile number or electronic mail address) must be updated, it will be documented onto the subject code list and contact info log. Unstructured notes about the telehealth sessions will be documented onto the CRFs by the session facilitator(s) and may include individual participants' level of engagement and involvement during the session, as well as noted significant changes in patient's home circumstances, life events, travel, or major illnesses.
 - 2.Twice monthly weights will be entered into the scale's app will be recorded as well.
 - 3. Missed telehealth sessions will be tallied at the final study visit for each telehealth group participant.
 - 4. Questionnaires assessing quality of life, self-efficacy, diet, and physical activity habits will be administered and collected at baseline, 3-month, and 6-month visits; at the 6-month end point they will also complete a survey about satisfaction with care. It is anticipated that it will take participants 30 to 60 minutes to complete these questionnaires, in addition to a brief visit with research staff to obtain their measurements.

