 - 5.A1C, fasting glucose, fasting lipids, AST and ALT will be drawn at 6-month visit, and results will be documented as well. They will also be drawn at baseline, if participants did not have them performed as part of their clinical care during the previous 6 months. Baseline lab results will also be documented.

6.General session information for bi-weekly (every 2 weeks) telehealth sessions will be collected onto the Telehealth Session Report forms by the session facilitators, including which participants attended and how the facilitator felt the session went.

 Experimental procedures for Control Group subjects will be limited to data abstraction from the CHLA KIDS electronic medical record (EMR

Statistical Plan

As noted previously, the target recruitment of 32 intervention and 176 control was arrived at based on practicality and feasibility for a pilot study. For evaluation of changes in the continuous outcomes, BMI, blood pressure, and hemoglobin A1C, triglyceride level, and ALT, assessed at baseline and immediately following the end of the 6 month intervention, we will utilize regression methods, which will allow us to compare the magnitude of change between the telehealth intervention and the comparison group, taking into account both change from baseline to follow-up time points as well as relevant baseline covariates. For these analyses covariates will be participants' age, gender, and presence of existing medical conditions (e.g. diabetes; rheumatologic conditions) that could affect weight loss.

Update June 2021: Matched control group subjects will be identified by calculating a propensity score, by collecting data for all potential control patients seen in EMPOWER clinic in the approved date ranges. There is no change to the nature of the data points, and their data will be extracted from KIDS and entered into REDCap database as already outlined.

Update Dec 2022: Given the limited data available for each of the matched clinic control patients (many had missing lab and other values), it was determined that we should remove the "matched" inclusion criteria and collect data on all 176 eligible control patients, in order to have a statistically meaningful cohort.

Data Handling and Record Keeping

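### Once matching was dropped, severity of obesity became the only former matching factor with no explicit control in the non-randomised efficacy comparison

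*Combined protocol and SAP*

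**What the plan says.** - **Comparability factors.** The control-group paragraph of the opening summary describes controls "matched to the intervention group for age, gender, and severity of obesity".
- **Matching method.** The June 2021 update in the Statistical Plan says matched controls will be found with a propensity score. It does not list the variables in that score.
- **Matching removed.** The December 2022 update explains that "many had missing lab and other values" among matched controls, and so the team should drop the matched "inclusion criteria and collect data on all 176 eligible control patients". The Inclusion Criteria agree. The retrospective group is "All eligible youth from our EMPOWER clinic patients whose first clinic visit occurred between January 2015 and June 30, 2019", aged 14-18, with no mention of matching.
- **Covariates.** The Statistical Plan and the statistics paragraph of the opening summary give the same list: "age, gender, and presence of existing medical conditions (e.g. diabetes; rheumatologic conditions) that could affect weight loss". The regression compares change from baseline in BMI, blood pressure, A1C, triglycerides and ALT. Neither severity of obesity nor baseline BMI is named, and no propensity weighting replaces the matching.
- **Role of the comparison.** Efficacy is the tertiary aim. The stated expectation is that telehealth will do as well as in-person care or better.

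**The concern.** In a comparison with retrospective clinic controls, confounding is limited only by how the controls are selected and by what goes into the regression. The sponsor chose three factors for selection. When selection by matching was abandoned, two of them were still in the regression and the third was not. The reason recorded for dropping matching was missing data, not a judgement that severity does not matter.

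Shared eligibility does not equalise severity. "These criteria include body mass index (kg/m2) that is either greater than the 99th percentile, or greater than the 95th percentile" with a comorbid condition: these are two floors, and the mix of severity above them can differ between two fully eligible groups. The groups also arise differently. Controls are Empower clinic patients. Telehealth participants may come from Empower and KidsNFitness referrals, "as well as CHLA patients seen in a multitude of environments, including outpatient clinics, the Emergency Department" and other services. If the severity mix differs and severity is related to change, the telehealth-versus-clinic estimate carries that difference and presents it as a treatment effect or masks one.

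**Working it through.** **1. Set the lists side by side.**

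| Factor | Matching factor (opening summary) | Regression covariate (Statistical Plan) |
|---|---|---|
| Age | yes | yes |
| Gender | yes | yes |
| Severity of obesity | yes | no |
| Existing medical conditions | no | yes |

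With matching removed, severity is the only factor in the second column without an entry in the third.

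**2. How much could it matter?** The plan gives no power, alpha, SD or imbalance, so there is no figure to reproduce and what follows is an illustration.

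- From the Statistical Plan: 32 intervention and 176 control.
- Assumed: two-sided 0.05 and no true effect.
- Assumed: d, the severity difference in SD units left after age, gender and conditions.
- Assumed: r, the within-group correlation of severity with change.

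Standard error of the group difference, in SD of change: sqrt(1/32 + 1/176) = sqrt(0.03125 + 0.00568) = 0.192.

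Shift from omitting severity: r × d. False-positive rate: P(|Z| > 1.96) when Z is centred at r × d / 0.192.

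| d | r | shift (SD of change) | shift / 0.192 | false positives |
|---|---|---|---|---|
| 0.25 | 0.1 | 0.025 | 0.13 | 5.2% |
| 0.25 | 0.2 | 0.05 | 0.26 | 5.8% |
| 0.25 | 0.3 | 0.075 | 0.39 | 6.8% |
| 0.5 | 0.1 | 0.05 | 0.26 | 5.8% |
| 0.5 | 0.2 | 0.10 | 0.52 | 8.2% |
| 0.5 | 0.3 | 0.15 | 0.78 | 12.2% |

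At d = 0.1 and r = 0.3 the shift is 0.03 and the rate 5.3%. If the conditions covariate absorbs half of d = 0.5, the d = 0.25 rows apply.

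**3. Can adding severity do harm?** Yes, if the groups differ by a stable amount that does not regress to a common mean. Let rho be the correlation between an outcome's baseline and follow-up, and c the correlation of severity with that baseline.

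- *Omitting severity, when groups regress to a common mean:* r = c × sqrt((1 − rho)/2), used as in step 2.
- *Adding severity, when the difference is stable:* bias c(1 − rho)d, residual variance 2(1 − rho) − (c(1 − rho))², standard error the root of that variance times sqrt(1/32 + 1/176 + d²/206), where 206 = 208 − 2.

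For c = 0.3, d = 0.5, rho = 0.5:

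- Omitting: r = 0.15, shift 0.075/0.192 = 0.39, giving 6.8%.
- Adding: bias 0.075, standard error sqrt(0.9775) × 0.195 = 0.193, giving 6.7%.

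At rho = 0.7 and 0.9 the pairs are 6.1% against 6.0%, and 5.3% against 5.3%. On the same inputs the two risks are practically equal.

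For BMI, severity is the outcome's own baseline, so c = 1. Over rho 0.9 to 0.5:

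| d | omitting | adding |
|---|---|---|
| 0.25 | 6.0-10.0% | 6.0-11.6% |
| 0.5 | 9.0-25.5% | 9.0-31.5% |

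**4. Precision cost of the extra term.** The ratio sqrt(1/32 + 1/176 + d²/206)/0.192 is 1.004 at d = 0.25 and 1.016 at d = 0.5, before any gain from explained variance.

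**The case against.** **The harm is hypothetical.** No severity imbalance is reported, and efficacy is the tertiary aim of a pilot sized on practicality. This stands, and it limits how hard the point can be pressed. The figures also use all 32 participants. With 24 completers (12 per cohort, as in the Overview Design Summary) against 176, the 12.2% becomes 10.6%. With 24 against an assumed 60 usable controls it is 9.5%.

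**Severity is partly handled already.** The conditions covariate is open-ended, and a comorbid condition is the entry route between the 95th and 99th percentiles, so it may track severity in part. This also stands, but tracking in part is not control.

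**The plan accounts for change from baseline.** A change score does not adjust for baseline level. If the wording were read as adjusting for each outcome's own baseline, severity would be covered for BMI only.

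**The propensity score may not have included severity.** Its variables are not listed, so severity's place in it is inferred. The opening summary nevertheless names severity as a matching factor.

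**Adjustment is not automatically safer.** A reader might infer that adding severity carries less risk than leaving it out. The working does not bear that out: on equal inputs the risks are practically the same, and for BMI adding is no safer. The case for adding severity to the other four outcomes is that it restores control of a factor the sponsor chose. It is not that the error rate is shown to be lower.

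**Conclusion.** The point holds as a gap in the plan. One of the sponsor's own three comparability factors lost its control when matching was removed, and nothing explicit replaced it.

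Its size is modest and conditional. Under the assumed inputs, false positives are 5.2-6.8% at a residual imbalance of 0.25 SD and 5.8-12.2% at 0.5 SD, against a nominal 5%. At 0.1 SD the gap is negligible. This rests on assumed values of d and r, a linear relation, and full use of 32 and 176. It affects how the efficacy comparison is read, not the feasibility aim.

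Three stronger readings are not supported:

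- That the comparison is biased. Imbalance is plausible, but its size and direction are not documented.
- That one BMI model, with or without baseline severity, is the right one. Either can be biased in non-equivalent groups.
- That the plan errs by not saying whether each other outcome's own baseline value is in the model. That is an unstated choice, and this point does not depend on it.

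**What to change.** In the Statistical Plan, and in the identical covariate sentence of the opening summary:

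1. For blood pressure, A1C, triglycerides and ALT, add one baseline BMI severity measure, named before analysis, to the covariates. Report the model without it as a sensitivity analysis.
2. For BMI, name in advance which model is primary, with or without baseline severity, and report both.
3. Tabulate baseline severity by group with standardised differences. This alone would show whether the imbalance exists.

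Removing the leftover matching wording from the control-group paragraph of the opening summary, so that it agrees with the Inclusion Criteria and the December 2022 update, is editorial.

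The cost is plan wording, a little analysis time, one degree of freedom per model, and a standard error about 0.4% (d = 0.25) to 1.6% (d = 0.5) larger before any gain from explained variance. No new data collection is needed. BMI is already an outcome in both groups, and the telehealth data collection includes "weight/body mass index (BMI), blood pressure, medications, and lab results, onto the CRFs". Any control without a recorded baseline BMI would drop out of the adjusted models, so that number should be reported.

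### One covariate list, chosen for its bearing on weight loss, serves all five outcomes and does not name the baseline value of the outcome

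*Combined protocol and SAP*

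**What the plan says.** The Statistical Plan covers the five outcomes in one sentence, which opens "For evaluation of changes in the continuous outcomes, BMI, blood pressure, and hemoglobin A1C, triglyceride level, and ALT". Regression is to compare the size of change between the arms, "taking into account both change from baseline to follow-up time points as well as relevant baseline covariates". The next sentence gives the list: "For these analyses covariates will be participants' age, gender, and presence of existing medical conditions (e.g. diabetes; rheumatologic conditions) that could affect weight loss". The statistics paragraph of the opening summary repeats it, with the same third item: "presence of existing medical conditions (e.g. diabetes; rheumatologic conditions) that could affect weight loss". No outcome-specific list appears elsewhere, and the baseline value of the outcome is not named.

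Under Inclusion Criteria, patients above the 95th but not the 99th BMI percentile qualify with an "obesity-related comorbid condition such as hyperlipidemia, pre-diabetes or diabetes, non-alcoholic fatty liver disease (NAFLD), obstructive sleep apnea, or polycystic ovarian syndrome".

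The telehealth arm attends "in-person research visits at 0, 3 and 6 months for collection of weight, blood pressure, and other anthropometric measures". Under Intervention Visits, data are also taken from referral packets or the medical record "regarding their weight/body mass index (BMI), blood pressure, medications, and lab results, onto the CRFs", and "Baseline lab results will also be documented". For controls the plan specifies only abstraction from the hospital record and does not list the fields. The December 2022 update under Statistical Plan drops matching, because many matched controls lacked laboratory and other values, and takes all 176 eligible controls instead.

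**The concern.** The comparison is not randomised. Controls are EMPOWER clinic patients first seen between January 2015 and June 2019. Telehealth participants may also come from other outpatient clinics, the Emergency Department and inpatient services, so a different case mix is plausible. The opening summary names age, gender and severity of obesity as matching factors. With matching removed, regression is the only stated control for confounding, and severity is not on the covariate list.

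This leaves three gaps.

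- **Baseline value.** Taking a change from baseline is not the same as adjusting for baseline. Leaving the baseline value out of the model gives up precision. It also leaves unstated which assumption about the two arms the estimate rests on.
- **Selection rule.** Conditions qualify by their effect on weight loss, but four of the five outcomes are not weight measures. Under that rule, whether hyperlipidemia enters the triglyceride model or NAFLD the ALT model depends on the wrong question.
- **Coding.** If all conditions share one yes/no term, the A1C model gives diabetes and rheumatologic disease the same coefficient. A difference between arms in the share with diabetes may then be only partly adjusted.

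**Working it through.** **Inputs.** The arm sizes, 32 and 176, come from the Statistical Plan (the opening summary's statistics paragraph has about 30 and 176). The plan states no SD, correlation, effect size or error rate, so there is no figure of its own to reproduce. Assumed here: baseline to follow-up correlation r of 0.5 to 0.7, equal SDs at the two times and in the two arms, a baseline gap of 0.3 SD, and the condition shares in step 3.

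**1. Precision.** The arm-size factor is sqrt(1/32 + 1/176) = 0.192. In SD units, the change-score SE is sqrt(2(1−r)) × 0.192 and the baseline-adjusted SE is sqrt(1−r²) × 0.192. Their ratio is sqrt((1+r)/2).

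| r | Change score | Baseline-adjusted | Ratio | Reduction |
|---|---|---|---|---|
| 0.5 | 1.000 × 0.192 = 0.192 | 0.866 × 0.192 = 0.166 | 0.866 | 13% |
| 0.7 | 0.775 × 0.192 = 0.149 | 0.714 × 0.192 = 0.137 | 0.922 | 8% |

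With 30 telehealth participants the factor is 0.198 and the ratios do not change. A 0.3 SD baseline gap adds about 0.3²/(32 + 176 − 2) = 0.0004 to 1/32 + 1/176 = 0.0369. This raises the adjusted SE by about 0.6%, so nearly all of the gain remains.

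**2. Difference between the two estimates.** The change score subtracts the whole baseline gap, and the adjusted estimate subtracts r times the gap. They differ by (1−r) × gap: 0.5 × 0.3 = 0.15 SD at r = 0.5, and 0.3 × 0.3 = 0.09 SD at r = 0.7. This is an error in the change score only if both arms regress to a common mean.

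**3. Merged or separate diabetes term.** Let D be the effect of diabetes on A1C change, and let other conditions have no effect. With one merged indicator, bias = D × [difference in diabetes share − b × difference in merged share]. Here b is the pooled within-arm slope of diabetes on the merged indicator. Example, second row of the table:

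- b = (32 × 0.10 × 0.85 + 176 × 0.20 × 0.75) / (32 × 0.15 × 0.85 + 176 × 0.25 × 0.75) = 29.12/37.08 = 0.785
- bias = D × (−0.10 + 0.785 × 0.10) = −0.02D

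| Diabetes, telehealth v control | Other conditions | No condition term | Merged | Separate |
|---|---|---|---|---|
| 10% v 10% | 5% v 5% | 0 | 0 | 0 |
| 10% v 20% | 5% v 5% | −0.10D | −0.02D | 0 |
| 5% v 15% | 10% v 10% | −0.10D | −0.04D | 0 |
| 5% v 20% | 15% v 5% | −0.15D | −0.11D | 0 |
| 5% v 15% | 10% v 0% | −0.10D | −0.10D | 0 |

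A merged term leaves most of the imbalance in place only when the other conditions offset it, as in the last two rows.

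**4. Availability.** Anyone who contributes a change score has a baseline value, so baseline adjustment excludes nobody in either arm. Diagnoses differ. The telehealth list itemises BMI, blood pressure, medications and laboratory results but not diagnoses, and the control fields are not itemised. Patients above the 99th percentile need no comorbidity to qualify, so eligibility data alone will not supply diagnoses.

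**The case against.** The strongest reply is that the plan leaves these matters open and is not wrong about them. It promises relevant baseline covariates in general terms, and its examples of medical conditions are introduced as examples. Several stronger readings do not stand.

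- **That diabetes is merged with unrelated disease.** The coding is not specified, and separate indicators fit the wording equally well. Even a merged term removes about 80% of the imbalance in the second row of the table.
- **That the blood pressure, triglyceride and ALT models omit their main determinants.** The documents rank no determinants, and the open list does not exclude hyperlipidemia or NAFLD. The outcome is also a change, so a stable influence on level may largely cancel. The documents give nothing from which to size an effect on change.
- **That everything needed is already recorded.** This is itemised for telehealth only, and many matched controls had missing values.
- **That a mixed diabetes population shows the cost of the covariate list.** Assume 5 to 20% with diabetes and a change SD of 1.0 to 1.5 points, against 0.3 in the rest. The 95% half-width is then 0.14 to 0.27 points overall, against 0.12 to 0.13 without diabetes, a ratio of 1.2 to 2.2. That is unequal variance. The calculation gives both groups the same mean change, so a diabetes term would not narrow the interval.
- **That a change score is biased whenever baselines differ.** This requires regression to a common mean, which cannot be taken for granted in non-randomised groups.

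Efficacy is also only the tertiary aim of a pilot. These points limit the concern. They do not remove the precision gain, or the mismatch between a weight-loss rule and four other outcomes.

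**Conclusion.** The point holds as a gap in specification. One list serves five outcomes, it does not name the baseline value of the outcome, and its selection rule suits only BMI. Baseline adjustment is the firmest part: it shortens the SE by about 8 to 13% at an assumed r of 0.5 to 0.7 and uses data already in hand. The choice of estimator can also move the result by 0.09 to 0.15 SD per 0.3 SD baseline gap. That shift may be called a bias only under the common-mean assumption.

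The diabetes part is conditional. In the assumed scenarios the bias from a merged indicator runs from 0 to 0.11D, and it is 0 when condition shares match. The documents do not say that the indicator is merged. No size can be given for leaving hyperlipidemia or NAFLD out.

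**What to change.** Amend the Statistical Plan, and the matching sentences in the opening summary, as follows.

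1. In each model, adjust for the baseline value of that outcome: systolic pressure in the systolic model, diastolic in the diastolic model, and likewise BMI, A1C, triglycerides and ALT. State the assumption this makes about regression to the mean in non-randomised groups.
2. Select medical conditions by whether they could affect the outcome being modelled, and state how they are coded.
3. Enter diabetes as its own indicator in the A1C model. Describe A1C change by diabetes status without inference: at an assumed 5 to 20%, the telehealth arm would hold about 2 to 6 people with diabetes (32 × 0.05 = 1.6; 32 × 0.20 = 6.4).
4. Add hyperlipidemia to the triglyceride model and NAFLD to the ALT model only if these diagnoses can be abstracted the same way in both arms.

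Item 1 needs no new data. Items 3 and 4 need diagnoses abstracted from the records, and missing control data may limit item 4. Each model loses one or two degrees of freedom, and with 32 telehealth participants further terms should be added sparingly.

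### Control lab changes exist only where routine care gave two values, and the change regression omits the baseline lab; if re-testing followed high results, the comparison favours controls

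*Combined protocol and SAP*

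**What the plan says.** Lab values reach the analysis by different routes in the two arms.

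- **Telehealth, follow-up.** The list of data collected under Intervention Visits schedules a study draw: "A1C, fasting glucose, fasting lipids, AST and ALT will be drawn at 6-month visit, and results will be documented as well".
- **Telehealth, baseline.** A recent clinical result is used where there is one. Otherwise blood is drawn for the study, "if participants did not have them performed as part of their clinical care during the previous 6 months".
- **Controls.** There is no study draw at either time: "Experimental procedures for Control Group subjects will be limited to data abstraction from the CHLA KIDS electronic medical record (EMR".

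The December 2022 update in the Statistical Plan says of the matched controls that "many had missing lab and other values". Its response is to drop matching and take all 176 eligible controls.

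For BMI, blood pressure and the three labs, the plan "will utilize regression methods, which will allow us to compare the magnitude of change between the telehealth intervention and the comparison group". It mentions relevant baseline covariates in general terms and then names them: "age, gender, and presence of existing medical conditions (e.g. diabetes; rheumatologic conditions) that could affect weight loss". The baseline value of the outcome is not named. The statistics paragraph in the opening summary has the same model and the same list. Neither place gives a missing-data method or a sensitivity analysis.

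**The concern.** A control has a change in A1C, triglycerides or ALT only if clinicians happened to obtain both values, whereas a telehealth participant who attends at 6 months has the second value by design. The groups compared may therefore be selected differently.

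The selection matters if it depends on the baseline result. A patient re-tested because a value was high will on average have a lower value next time, even if nothing has changed. A change score with no baseline adjustment counts that fall as improvement. If it happens mainly among controls, it is credited to in-clinic care and could hide a telehealth benefit on these labs. Adding controls from the same charts narrows the confidence interval around the same biased quantity.

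**Working it through.** **No plan figure to reproduce.** The documents give no re-test rate, lab SD, baseline/follow-up correlation, effect size or power. Sample size rests on practicality: "the target recruitment of 32 intervention and 176 control was arrived at based on practicality and feasibility for a pilot study". What follows shows how large the bias would be under stated assumptions.

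**Inputs.** From the Statistical Plan: 32 telehealth, 176 controls, change as outcome, baseline lab not a covariate. Assumed: correlation ρ of 0.5, 0.7 or 0.85; share of controls re-tested f of 0.25, 0.5 or 0.75; the rule for re-testing; no true change in either group; no selection on baseline in the telehealth group.

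**Formula.** Let baseline B and follow-up Y have mean 0, SD 1 and correlation ρ. Then E[Y − B | B] = −(1 − ρ)B. If only the top share f is re-tested, the cut-off is c = Φ⁻¹(1 − f) and the mean baseline of those re-tested is φ(c)/f. So

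control mean change = −(1 − ρ) × φ(c)/f.

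For f = 0.5: c = 0, φ(0) = 0.399, and 0.399/0.5 = 0.798. With ρ = 0.7 the change is −0.3 × 0.798 = −0.239 baseline SD.

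| ρ | f = 0.25 | f = 0.5 | f = 0.75 |
|---|---|---|---|
| 0.5 | −0.636 | −0.399 | −0.212 |
| 0.7 | −0.381 | −0.239 | −0.127 |
| 0.85 | −0.191 | −0.120 | −0.064 |

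The number of controls does not appear in the formula, so taking all 176 leaves the bias where it was. By symmetry, re-testing only the lowest values gives the same sizes with the opposite sign.

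**Simulation.** 2,000 runs per scenario, two-sided 5% test, change regressed on arm and a listed condition, without and then with the baseline lab. The difference is telehealth minus control change in baseline SD; a positive value is a spurious advantage to controls. At ρ = 0.7 and f = 0.5:

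| Re-testing of controls | Difference, no baseline lab | False-positive rate | Difference, baseline lab added | False-positive rate |
|---|---|---|---|---|
| Unrelated to baseline | 0.003 | 6.0% | 0.003 | 6.2% |
| Depends only on a listed condition | 0.001 | 5.1% | 0.002 | 5.8% |
| Graded, odds ratio 3 per SD | 0.130 | 13.8% | −0.003 | 5.1% |
| Graded, listed condition also predicts the lab | 0.124 | 12.9% | −0.004 | 5.7% |
| Top half only | 0.233 | 32.9% | −0.007 | 4.4% |

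The simulated 0.233 agrees with the analytic 0.239. Over all ρ and f, graded re-testing gave 0.04 SD (7% false positives) to 0.32 SD (30%), and strict top-share re-testing gave 0.06 SD (10%) to 0.63 SD (81%).

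With the baseline lab in the model, every scenario gave a difference between −0.01 and 0.01 SD and a false-positive rate of 4.3% to 6.2%. The simulation error of a 5% rate is √(0.05 × 0.95/2000) = 0.5 percentage points. Adjustment works here because, given B, the expected follow-up value is the same whether or not selection used B.

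**The case against.** The strongest objection is that nothing in the documents shows that high values prompted re-testing. A reader might infer that the planned regression does credit controls with regression to the mean. The documents do not support that: they give neither the reason for the missing values nor the time point, and the quoted remark concerns the matched controls and covers other values besides labs. Existing conditions, with diabetes as an example, are already covariates, and the bias vanishes if re-testing depends only on those. This stands, and it makes the point conditional.

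A reader might also infer that telehealth labs will be complete and free of the same effect. Attrition is expected, baseline values may be clinically ordered results up to 6 months old, and the Inclusion Criteria admit some patients on conditions such as hyperlipidemia or pre-diabetes. Telehealth values can regress too, which would offset some of the bias. The calculation gives that group no such selection, so its figures lie towards the upper end for each mechanism.

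A third inference would be that the number of controls analysed for labs falls far below 176. Some shortfall is likely, but no count is given.

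Finally, this is a pilot, efficacy is the tertiary aim, and the supposed bias works against telehealth, so it would not create false superiority. That limits the importance. It does not justify omitting a covariate that is already being collected, particularly when the stated expectation is that telehealth will do as well as, or better than, in-person care.

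**Conclusion.** The concern holds in conditional form. The documents establish three things: different lab ascertainment by arm, incomplete control labs, and a change regression that does not list the baseline lab. If re-testing of controls tracked high baseline values beyond the listed conditions, the A1C, triglyceride and ALT comparisons would be biased in favour of controls.

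With half re-tested and ρ = 0.7, the bias is about 0.13 baseline SD under graded re-testing and 0.24 SD if only the top half are re-tested. It is nil if re-testing is unrelated to baseline or depends only on a listed condition, and it reverses if low values are favoured. The correlation, the share re-tested and the mechanism are all assumptions. The argument does not carry over directly to BMI and blood pressure, where follow-up depends on return visits.

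The change is worth making because it is nearly free and removed the bias in every scenario examined, not because the bias has been shown to exist.

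**What to change.** In the Statistical Plan, and in the matching statistics paragraph of the opening summary:

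1. Add the baseline value of the same lab as a covariate in each of the A1C, triglyceride and ALT regressions. Anyone with a change score already has this value, so no participant is lost; the cost is one coefficient per model.
2. Report, per arm and per lab, the number with both values.
3. Tabulate baseline labs of controls with and without a repeat. This shows directly whether re-testing tracked the baseline.
4. State how missing labs are handled. Multiple imputation may be added as a sensitivity analysis. With at most 32 telehealth participants it should stay simple, and agreement with the complete-case result would not validate the missing-at-random assumption, since both can be biased the same way.
5. State the remaining limitation with the results: baseline adjustment does not repair re-testing driven by the patient's interim course or by retention, nor missing baseline labs.

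This is analysis and reporting work on data already being abstracted. It needs no new blood draws.
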